11.3. Special Considerations

11.3.1 Adverse Events of Special Interest

Since topical retinoids are associated with local application site AEs, particularly when beginning treatment, these events will be followed closely during the study and considered AEs of special interest (AESIs).

11.3.2 Pregnancy

All WOCBP who participate in the study should be counseled on the need to practice highly effective birth control and on the importance of avoiding pregnancy during study participation. Women should be instructed to contact the investigator or study staff immediately if pregnancy occurs or is suspected.

Pregnancy testing will be conducted prior to administration of the IP on every woman of childbearing potential. A woman who is found to be pregnant at the Screening Visit will be excluded from the study and considered to be a screening failure.

A woman who becomes pregnant during IP treatment will be immediately discontinued from study treatment. The investigator must report the pregnancy of any woman who becomes pregnant during or within 30 days after discontinuing treatment as if it were an SAE within 24 hours of learning of the pregnancy, to Premier Research Pharmacovigilance using the Pregnancy Data Collection Form via the same fax number and/or email address as for SAE reporting. The

investigator should contact the designated individual(s) who receive SAE notification and record information related to the pregnancy on an SAE and AE form (entering the event temporarily as nonserious on both forms) provided by the sponsor or its designee. If a partner of a male study subject becomes pregnant, the investigator must report the pregnancy as soon as possible after learning of it to the Premier Research Pharmacovigilance using the Pregnancy Data Collection Form. A separate pregnant partner ICF will be required.

Early Termination Visit assessments are required as soon as possible after learning of the pregnancy in a study subject. The investigator is also responsible for following the pregnancy until delivery or termination. These findings must be reported on the Exposure in Utero form and forwarded to the designated individual(s). The event meets the SAE criterion only if it results in a spontaneous abortion or a congenital anomaly.

Among the clinical studies, 12 pregnancies were reported: 4 resulted in normal births; 5 resulted in spontaneous abortions (none of which was considered related to CD5789); 1 was electively aborted, and 2 were lost to follow-up (Investigator's Brochure for CD5789 Cutaneous Formulation).

12. DATA SAFETY MONITORING BOARD

Safety oversight will be under the direction of a DSMB composed of individuals with the appropriate expertise, including LI. Members of the DSMB should be independent from the study conduct and free of conflict of interest, or measures should be in place to minimize perceived conflict of interest. The DSMB will operate under a charter that will be finalized prior to the start of the study. The DSMB will meet at least 3 times during the conduct of the study: when the study begins, when 15 adult subjects have enrolled in Cohort A and have completed at least 28 days of treatment, and after 60 subjects have enrolled in the study.

The DSMB will meet after 15 subjects in Cohort A have completed at least 28 days of double-blind treatment to review aggregate safety and tolerability data (including PK and ECG results). The safety data will be unblinded. At that time, the DSMB will decide whether Cohort B (adults and subjects aged 12–17) may begin enrolling, or if additional adult safety data are required before allowing subjects aged 12 – 17 to participate in the study. The DSMB will have the authority to recommend to the sponsor that the study be modified, placed on hold, or stopped if serious safety issues are discovered. The DSMB will provide its input to Mayne Pharma LLC. Any protocol changes the DSMB may suggest will be submitted to all applicable regulatory bodies for review and approval.

In case of significant toxicity, the DSMB may choose to review the available safety data and recommend stopping recruitment in a particular dose group.

Stopping rules for individual subjects are in Section [9.4.1](#).

13. STATISTICS

13.1. Statistical Analysis

This section presents a summary of the planned statistical analyses. A SAP that describes the details of the analyses to be conducted will be written prior to database lock.

Unless otherwise indicated, all testing of statistical significance will be two-sided, and a difference resulting in a P value of ≤ 0.05 will be considered statistically significant.

Summary statistics will be provided for the variables described below. For continuous variables, these statistics will include the number of subjects, mean, standard deviation (SD), median, minimum, and maximum. For categorical variables, these statistics will include the number and percentage of subjects in each category.

The primary analysis period is the first 12 weeks of treatment (i.e., the Double-blind Period). Overall unblinding will take place at the end of the Double-blind Period of the study only after the database is locked. A second analysis will take place for endpoints assessed from Week 12 through the OLE Period. The baseline for the safety and efficacy parameters will be measured at Visit 1 or Visit 2, per the Schedule of Events for both the Double-blind Period (Table 2-1) and OLE (Table 2-2).

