Application instructions, advice on emollient and sunscreen use ⁱ	X	X	X	X			

	Open-label Treatment Period						Follow-up
	Telephone Visit (Day 97) ^a	Day 104 ± 5 days	Day 120 ± 7 days	Telephone Visit (Day 134)	Day 150 ± 7 days	Day 180 ± 7 days/ET	Day 194 or 14 days after End of Open-label Treatment
Visit		7	8		9	10	11
Week		14	16		20	24	26
Dispense study drug and diaries ^l		X	X		X		
Concomitant medications	X	X	X	X	X	X	X
Tolerability assessment		X	X		X	X	
Adverse events (and review diaries)	X	X	X	X	X	X	X
Collect all used/unused study drug ^k		X	X		X	X	

Abbreviations: ECG = electrocardiogram; ET = early termination; HEENT = head, eyes, ears, nose, throat; ICF = informed consent form; IGA = Investigator’s Global Assessment; PK = pharmacokinetic; OLE = open-label extension; VIIS = Visual Index for Ichthyosis Severity; WOCBP = women of childbearing potential

- a. Subjects will sign the OLE ICF at the Double-blind Day 90/Week 12 Visit or within 7 days thereafter. All efficacy assessments, safety/tolerability assessments, including clinical laboratory testing and PK from Day 90/Week 12 will be carried over for the OLE and will not be repeated.
- b. Limited physical examination to include HEENT, cardiorespiratory, abdomen, range of motion.
- c. IGA: 0 = clear; 1 = almost clear; 2 = mild; 3 = moderate; 4 = severe
- d. VIIS scale for each body area: chest/abdomen, back, legs, and arms, for a possible overall score = 16.
- e. Roughness (0-4 scale); fissuring assessment on palms/soles: present/absent/number/pain (0-3 scale).
- f. Subjects must be fasting (at least 8 hours)
- g. Subjects who are premenstrual at Screening but begin menses during the course of the study should follow the pregnancy testing schedule for WOCBP correlating to the visit menses began.
- h. Samples for PK will be drawn from all subjects at Day 120 and Day 180. Visits for PK must occur at least 24 hours after the last application of the IP to avoid contamination of the blood samples with any IP that may have remained in the skin after the last application.
- i. Subjects must record days/times of study drug application in the diaries and any areas of skin not treated (e.g., due to local reactions).
- j. All subjects in the OLE will receive trifarotene 200 µg/g. Study drug provided in 50-g tubes (maximum single application is 36 g). Measure study drug tubes before dispensing. Dispense enough additional study drug until the next visit (except at Day 180).

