6.2. Secondary Objectives

The secondary objectives are as follows:

- To assess systemic exposure to trifarotene and its major metabolites after topical application of the investigational product (IP) on up to 90% BSA twice weekly.
- To assess safety for up to 24 weeks of dosing with open-label trifarotene cream HE1 200 µg/g.

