9. TREATMENTS

9.1. Identification of Investigational Product(s)

Trifarotene cream HE1 is a cream containing 100 or 200 µg/g (0.01% [w/w] or 0.02% [w/w], respectively) of CD5789 and the following excipients: purified water, propylene glycol, allantoin, glycerin, medium-chain triglycerides, polypropylene glycol 15 stearyl ether, cyclomethicone, phenoxyethanol, copolymer of acrylamide and sodium acryloyldimethyltaurate, dispersion 40% in isohexadecane (simulgel 600 PHA), sodium benzoate, butylated hydroxytoluene, and gluconolactone. It is a potent RAR γ agonist characterized by its high specificity to this receptor.

Vehicle contains the same ingredients, without the CD5789.

Trifarotene cream HE1 and vehicle will be provided in cream form for topical application and will be supplied in 50-g tubes from which a maximum of 36 g of IP may be extracted,

Trifarotene cream HE1 and vehicle will be supplied by G. Production, Inc. (Galderma) in Baie-D'Urfé, QC, Canada.

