9.6. Method of Assigning Subjects to Treatment Groups

In the double-blind, parallel-group, randomized period of the study, subjects who meet study entry criteria will be randomly assigned in a 1:1:1 ratio to trifarotene cream HE1 100 µg/g or 200 µg/g or vehicle cream. The randomization schedule will be computer generated using a permuted block algorithm and will randomly allocate IP to randomization numbers. The randomization numbers will be assigned sequentially through a central interactive web response system (IWRS) as subjects are entered into the study. Study center will not be a blocking factor in the randomization schedule.

Premier Research will prepare the randomization schedule before the start of the study. No one involved in the study performance will have access to the randomization schedule before the official unblinding of treatment assignments. No subject will be randomized into this study more than once.

In the OLE, all subjects will receive trifarotene cream HE1 200 µg/g.

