13.1.6.3 Clinical Laboratory Evaluations

Descriptive summaries (mean, SD, median, minimum, and maximum) of actual (absolute) values and changes from baseline values will be presented for clinical laboratory values for each treatment group at each time point in each period.

The number of subjects with clinical laboratory values categorized as below, within, or above normal ranges will be tabulated showing change from baseline (shift tables) for each clinical laboratory parameter by treatment group and by study visit in each period.

Laboratory values that are outside the normal range will also be flagged in the data listings and presented with the corresponding normal ranges. Any out-of-range values that are identified by the investigator as being clinically significant will also be shown in a data listing.

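### One baseline (Visit 1 or Visit 2) is fixed for the open-label extension too, so for subjects randomized to vehicle the extension's change and shift tables include the net change over 12 weeks without drug

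*Protocol*

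**What the plan says.** Section 13.1 of the protocol states that the "baseline for the safety and efficacy parameters will be measured at Visit 1 or Visit 2", and the same sentence extends the rule "for both the Double-blind Period (Table 2-1) and OLE (Table 2-2"). Table 2-2 itself holds only Visits 7 to 11 and telephone contacts, so it supplies no other baseline.

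The rule feeds planned output in both periods:

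- **Laboratory (13.1.6.3):** changes from baseline, and categories that "will be tabulated showing change from baseline (shift tables) for each clinical laboratory parameter by treatment group and by study visit in each period".
- **Vital signs (13.1.6.4):** changes and shift tables by period.
- **IGA (13.1.4.2):** descriptive summaries and changes for both periods.
- **ECG:** Section 13.1.6.5 plans only values and normal/abnormal counts. Change from baseline for ECG comes solely from the general safety sentence in the synopsis.

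On treatment, Section 9.1 says "Vehicle contains the same ingredients, without the CD5789" and Section 9.6 says "In the OLE, all subjects will receive trifarotene cream HE1 200 µg/g". On the data at the start of the extension, footnote a to Table 2-2 says "All efficacy assessments, safety/tolerability assessments, including clinical laboratory testing and PK from Day 90/Week 12 will be carried over for the OLE". Section 10.2.2.7 makes that Day 90 visit the first visit of the OLE. No current section names Visit 6 as the OLE baseline.

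**The concern.** A safety table for a period in which everyone receives 200 µg/g will be read as showing what happened on that treatment. For subjects coming from vehicle, the last drug-free value is Day 90, not Day 1. With Day 1 as the reference, changes that came before the drug are shown in the OLE tables, and some changes that follow first exposure drop out of them.

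This bears on signals the protocol itself watches. Section 9.4.1 lists clinically significant changes in liver tests and lipids as a reason to stop treatment, and Section 5.2 notes that absorption in lamellar ichthyosis may exceed that in healthy volunteers. Ex-vehicle subjects are the group in whom onset on 200 µg/g can be observed against a drug-free, on-study value taken immediately before, and the stated baseline blurs that view.

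**Working it through.** The protocol gives no figure on this point, so there is none to reproduce. The check is an identity, two records, and two illustrations of size.

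**1. What the OLE change contains.**

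(OLE visit − Visit 2) = (Visit 6 − Visit 2) + (OLE visit − Visit 6)

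For a subject randomized to vehicle the first term arose without trifarotene. Only the second term covers time on 200 µg/g. With Visit 6 as baseline the first term disappears.

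**2. Two ex-vehicle laboratory records.** OLE laboratory tests are at Day 120 and Day 180; Day 120 is used here.

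| Day 1 | Day 90 (no drug yet) | Day 120 (on drug) | Tabulated with Visit 2 baseline | Tabulated with Visit 6 baseline |
|---|---|---|---|---|
| normal | high | high | normal to high: OLE shift | high to high: no shift |
| high | normal | high | high to high: no shift | normal to high: OLE shift |

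The misclassification runs in both directions.

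**3. IGA illustration.** Inputs: the Section 13.2 planning success rates of 40% on vehicle and 70% on each active arm, and 1:1:1 allocation of 120 subjects (40 per arm). Assumptions: arms enter the OLE equally, and open-label drug adds nothing after Day 90.

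- Ex-vehicle subjects already improved by at least two grades at Day 90: 0.40 × 40 = 16 of 40, or 40%.
- All entrants: (40 + 70 + 70) / 3 = 60%.
- The drug-free part of that 60% is only 16 of 120, or 13%. The rest was gained on trifarotene.
- With Visit 6 as baseline, all of these become 0% under the same assumptions.

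**4. Laboratory illustration.** None of these inputs is in the protocol. Assume a subject mean b ~ N(0, 0.8²), visit error N(0, 0.6²) (total variance 0.64 + 0.36 = 1), an upper limit of 1.96, no drug effect, and a drift d on vehicle that is present at both Visit 6 and Day 120. Let p₀(b) = P(Z > (1.96 − b)/0.6) and p_d(b) = P(Z > (1.96 − b − d)/0.6), and take expectations over b:

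- shifts by Visit 2 baseline: E[(1 − p₀) p_d]
- shifts by Visit 6 baseline: E[(1 − p_d) p_d]
- Visit 2 shifts already high at Visit 6: E[(1 − p₀) p_d²]
- Visit 6 shifts not shown with Visit 2 baseline: E[p₀ (1 − p_d) p_d]

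| Drift d | By Visit 2 | By Visit 6 | Ratio | Already high at Visit 6 | Visit 6 shifts not shown |
|---|---|---|---|---|---|
| 0 | 1.802% | 1.802% | 1.00 | 0.366/1.802 = 20% | 0.366/1.802 = 20% |
| 0.25 | 3.382% | 2.933% | 1.15 | 0.875/3.382 = 26% | 0.427/2.933 = 15% |
| 0.5 | 5.924% | 4.472% | 1.32 | 1.899/5.924 = 32% | 0.446/4.472 = 10% |

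Without drift the two totals agree, and about a fifth of the subjects counted are different people. Any inflation of the total comes from the assumed drift.

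**The case against.** The strongest reply is that a study-entry baseline matches the stated objective: "To assess safety for up to 24 weeks of dosing with open-label trifarotene cream HE1 200 µg/g". The extension lasts 12 weeks, so 24 weeks can only be reached by counting from Visit 2. This stands for subjects on 200 µg/g throughout. It does not help ex-vehicle subjects, who have at most 12 weeks of trifarotene.

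A second reply is that little is hidden. Observed values are shown by visit, and the first record above would already appear in the double-blind vehicle shift table. Out-of-range values are flagged in listings, and Section 10.3.4.1.3 requires clinically significant changes to be reported as adverse events whatever the baseline. This limits the harm. It does not correct the OLE tables, and the protocol does not define treatment group in the OLE as the randomized arm.

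A third reply is that the analysis plan could add a second baseline. It could, but it would then depart from an explicit protocol sentence.

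Several stronger readings are tempting and are not supported:

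- **Every change on vehicle is counted.** Only the net Visit 2 to Visit 6 change enters, and only in change and shift summaries.
- **Adverse event counts are contaminated.** They follow the treatment-emergent definitions in Sections 11.1.6 and 13.1.6.2, not this baseline.
- **The OLE will report a 60% response with no effect.** Section 13.1.4.2 confines the success proportion to the Double-blind Period, and no OLE responder endpoint is clearly planned.
- **ECG is affected as laboratory values are.** The ECG section plans no change and no shift table.

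**Conclusion.** The point holds as a stated rule that gives misleading OLE change and shift tables for ex-vehicle subjects, about one third of entrants if the arms enter equally. It is clearest for laboratory values and vital signs, applies to IGA change, and reaches ECG only through the synopsis.

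The direction of the error follows from the text alone. Its size does not. The 40% and 60% IGA figures are illustrations from the planning rates with equal entry and no further drug effect. The 20% to 32% laboratory shares rest on assumed standard deviations and drift, and the total is not inflated at all when drift is zero.

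The primary double-blind comparison is untouched, and Sections 13.1.4 and 13.1.6 rule out formal inference for OLE efficacy and for safety. The sentence should be corrected because the correction is simple, not because a main conclusion depends on it.

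**What to change.** In Section 13.1, separate the two periods:

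- **OLE safety baseline** (laboratory, vital signs, and ECG where change is shown): the last value before the first trifarotene application. That is Visit 2 for subjects randomized to either trifarotene concentration and Visit 6 (Day 90) for subjects randomized to vehicle.
- **Display:** present OLE change and shift tables by randomized double-blind arm. This also makes visible the 12 weeks on 100 µg/g that ex-100 µg/g subjects carry in their change from Visit 2.
- **OLE efficacy:** keep change from Visit 2 and add change from Visit 6.

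The cost is protocol and analysis-plan wording and some additional tables. Day 90 values are already collected and carried into the OLE, so no new data or visits are needed.

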13.1.1 Analysis Populations

The following 5 analysis populations are planned for the Double-blind Period of this study:

- Safety: all subjects who are randomized to treatment and receive at least 1 application of study drug in the Double-blind Period. This population will be the primary population for analyses of safety.
- Intent-to-treat (ITT): all randomized subjects. This population will be used as the primary population for the analysis of efficacy for the Double-blind Period of the study.
- Modified intent-to-treat (mITT): all subjects in the safety population with at least 1 postbaseline assessment of efficacy in the Double-blind Period.
- Per-protocol (PP): subjects in the mITT Population who met all inclusion criteria and no exclusion criteria, were compliant with study drug application, and who had no significant protocol deviations.
- Pharmacokinetic: all subjects in the Safety Population who have at least 1 plasma sample with quantifiable concentration. This population will be used to summarize all PK endpoints.

The following analysis populations are planned for the OLE of this study:

- OLE Safety: all subjects who complete the 12-week Double-blind Treatment Period and receive at least 1 application of study drug in the OLE.
- OLE ITT: all subjects who complete the 12-week Double-blind Treatment Period and sign the OLE informed consent.
- OLE mITT: all subjects in the OLE safety population with at least 1 assessment of efficacy after Visit 6.

- OLE PP: all subjects in the OLE mITT population who met all inclusion criteria and no exclusion criteria, were compliant with study drug application from baseline through EOT, and who had no significant protocol deviations throughout the study.

Inclusion in the analysis populations will be determined prior to database lock.

If a subject is randomized incorrectly or is administered the incorrect IP, analyses of the ITT and mITT populations will be based on the assigned treatment whereas all other analyses will be based on the actual treatment received.

13.1.2 Study Subjects and Demographics

13.1.2.1 Disposition and Withdrawals

For the Double-blind Period, the numbers of subjects randomized, completing Week 12 of the study, and withdrawing early from the Double-blind Period, along with reasons for withdrawal, will be tabulated overall and by randomized treatment group. The number of subjects in each analysis population will be reported. The number of subjects completing study milestones will also be tabulated by randomized treatment group. This analysis will be conducted for the ITT population.

For the OLE, the number of subjects entering the OLE, completing the study, and withdrawing early, along with reasons for withdrawal, will be tabulated overall. The number of subjects in each analysis population will be reported. The number of subjects completing study milestones will also be tabulated. This analysis will be conducted for the OLE ITT population.

13.1.2.2 Protocol Deviations

A protocol deviation is any noncompliance with the clinical study protocol or International Council for Harmonisation of Technical Requirements for Pharmaceuticals for Human Use (ICH) Good Clinical Practice (GCP) requirements. The noncompliance may be either on the part of the participant, the investigator, or the study site staff. As a result of deviations, corrective actions are to be developed by the site and implemented promptly.

It is the responsibility of the site investigator to use continuous vigilance to identify and report deviations promptly. All deviations must be addressed in study source documents, and reported to Premier Research or Mayne Pharma LLC. Protocol deviations must be sent to the reviewing IRB per their policies. The site investigator is responsible for knowing and adhering to the reviewing IRB requirements. Further details about the handling of protocol deviations will be included in the protocol deviation guidance plan.

Subjects who taper to once-weekly application or who take a “drug holiday” will not be reported as having deviated from the protocol.

13.1.2.3 Demographics and Other Baseline Characteristics

These analyses will be conducted for the ITT and OLE ITT populations.

Demographic variables will include age, sex, race, ethnicity, height, weight, and BMI. Baseline subject characteristics will include medical history, physical examination findings, and IGA score.

Prior and concomitant medications will be summarized by randomized treatment group, by the number and percentage of subjects taking each medication, and classified using World Health Organization Drug Dictionary (WHO-DD) Anatomical Therapeutic Chemical (ATC) classes and preferred terms.

